### **E. Internal Validity**

For all data and records that are a part of this study, a number (i.e. code) will be assigned to each participant. All collected blood samples will also be coded. This will minimize measurement bias when performing analysis on biochemical markers. The codes will only be broken once data analysis has been completed and verified by the PI.

### **F. Medical Safety Plan**

All aspects of the clinical study will be conducted in [name] clinical lab located in Campbell Hall. Participants will be fasted for 10-12 hours prior to each study visit. We recognize that certain risks associated with fasting include: hypoglycemia, weakness, and fainting. This duration of fasting is consistent with guidelines set forth by the American Diabetes Association to minimize risk to the individual when determining fasting blood glucose concentrations.

Risks related to hypoglycemia are anticipated to be low due to their underlying "healthy" health status and a prescribed diet for the three preceding days that will supply ~50% carbohydrate. In addition, shortly upon arrival to our study center, they will be ingesting a plant/spinach-based test meal. Throughout each visit to the study center, participants will be closely monitored by a member of the research team. These persons will monitor the safety and well-being of participants for any signs and symptoms of hypoglycemia including: confusion, dizziness, irritability, weakness, headaches, and fainting. Additionally, [name] (PI; [name]) has an academic office in close proximity to the study center and has significant experience coordinating clinical research studies involving overnight fasting, and other dietary-related meal challenges, thereby supporting the competency of our research team in managing potential adverse events relating to fasting glucose and glycemic responses.

Consistent with our prior studies of similar design, and to ensure participant safety, all blood collection procedures throughout each study visit will occur while positioned on a hospital bed in the prone position. In the event that a participant was to become weak, dizzy, or faint, they would already be ideally positioned to minimize risks associated with these symptoms. In the event that hypoglycemia-related symptoms occur, the study would be terminated to allow the participant to recover. We are prepared to provide pre-packaged beverages and snacks containing simple carbohydrates (e.g. Gatorade, fruit juice, apple sauce, crackers) that will allow for rapid restoration of blood glucose. These food items will be stored in a refrigerator that is located in close proximity and dedicated for foods used in research studies. Participant status (e.g. attentiveness, skin color) will be monitored in our clinical laboratory to ensure recovery. The clinical area where participants undergo blood draws is also equipped with first-aid measures (e.g. smelling salt) and all study team members are trained to assist with basic first-aid application if needed. Due to the amount of blood required for the study, participants will be advised not to donate blood and inform their doctor about the study if they need a blood draw at the doctor's office while they are on the study.

Any adverse hypoglycemic response that might occur during this study will receive care commensurate to the symptoms. For example, if a participant were to faint, then smelling salts would be administered along with a carbohydrate-containing food upon regaining consciousness. The study PI would also be contacted. Alternatively, should a more severe hypoglycemic response occur (e.g. contusion or laceration relating to fainting), the research team would immediately contact medical services (i.e. 911). For non-life threatening emergencies, any OSU students participating in these studies would be directed to the Wilce Student Health Center. For other emergencies or those participants who are not OSU students, individuals would be directed to the Wexner Medical Center either by transporting them directly or requesting ambulance service. Regardless of the complexity of the adverse events, the research team would monitor the participant in the interim, provide palliative care as appropriate, and follow-up after any medical care has been provided.

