**Test trials.** On **day 0** of each trial arm, participants will report to the study center in the fasted state (10-12 hours with no food or beverage except for water). They will return all empty food containers and/or uneaten portions. Arthrometric measurements will be performed. Then, a trained phlebotomist will collect a blood sample. Participants will then receive, in random order (determined with a random sequence generator; <http://www.random.org/sequences/>), one of the test meals to consume (see below table). Thereafter, blood samples will be collected at 3, 4.5, 6, 7.5, 9, and, 12 hours post-meal ingestion to isolate plasma and circulating lipoproteins for biochemical measurements (e.g. vitamin E, vitamin K). During each study visit, participants will have access to drinking water and can use the restroom as needed. A standardized lunch (after the 4.5-h blood draw) and dinner (after the 9-h blood draw) also will be provided.

For all test meals, deuterium-labeled spinach will be generated by [name] as described above. Harvested spinach will be stored in vacuum-sealed bags in a freezer dedicated for human foods. For each trial ~100 g of spinach will be used. In the Human Nutrition Metabolic Kitchen, spinach will be rinsed consistent with safe food handling practices and then steamed. Hardboiled eggs will also be prepared in egg cooker. These whole eggs in their entirety, or their egg white portion will be used to prepare the test meals. Whole eggs along with vegetable oil will be purchased from a local supermarket (e.g. Kroger).

	Study 1	Study 2	Study 3
Test Meal 1	Spinach + 0 hardboiled eggs (Time 0)	Spinach alone (Time 0)	Spinach + 0 hardboiled eggs (Time 0)
Test Meal 2	Spinach + 1 hardboiled egg (Time 0)	Spinach + 2 eggs whites (Time 0)	Spinach + 1 hardboiled egg (Time 0)
Test Meal 3	Spinach + 2 hardboiled eggs (Time 0)	Spinach + 2 whole eggs (Time 0)	Spinach + 2 hardboiled eggs (Time 0)
Test Meal 4	Spinach + 3 hardboiled eggs (Time 0)	Spinach + vegetable oil (Time 0)	Spinach + 3 hardboiled eggs (Time 0)
Test Meal 5	Spinach + 0 eggs (Time 0) + 1 egg (at 3 h)	Not applicable	Spinach + 2 hardboiled egg whites (Time 0)

Teat Meal 6	Spinach + 1 egg (Time 0) + 1 egg (at 3 h)	Not applicable	Spinach + vegetable oil (Time 0)
-------------	---	----------------	----------------------------------

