On **day 1** of each trial arm, they will report to the study center in the fasted state for blood collection at 24-h post-meal ingestion. They will return again for a non-fasting blood draw at 36-h post-meal ingestion.

On **day 2** of each trial arm, they will report to the study center in the fasted state for blood collection at 48-h post-meal ingestion.

On **day 3** of each trial arm, they will report to the study center in the fasted state for blood collection at 72-h post-meal ingestion. This is the terminal blood draw. Participants will then undergo at least 1-week washout before completing the remaining 3 trials within either study (see Table) in random order and in a manner identical to procedures described above.

**Sampling Handling.** Once at screening (8 mL), and 11-times during each pharmacokinetic trial (0, 3, 4.5, 6, 7.5, 9, 12, [16 mL/time point]; 24, 36, 48, and 72 h [8 mL/time point]), a blood sample will be collected. During each trial, a total volume of 144 ml (~0.6 cup) will be collected. Thus, 872 mL (~3.6 cups) will be collected in Study 1 (or Study 3) (screening + 6 trials) that spans at least 12 weeks. For Study 2, we calculate that 584 ml (~2.4 cups) of blood will be collected (screening + 4 trials) over a span of at least 8 weeks.

During each trial, plasma (0-72 h) and lipoproteins (0-72 h; chylomicrons, VLDL, LDL, HDL) will be obtained by centrifugation, and then transferred to appropriate storage tubes. Tubes will be stored at -80°C until analysis can be completed. Analyses of blood samples will include labeled and unlabeled α-T and PQ cholesterol, triglycerides, vitamin C, carotenoids, and oxidative stress biomarkers (i.e. malondialdehyde). No genetic materials are being collected or archived as part of this study. However, remaining blood sample aliquots not used for these analyses will be archived for 5 y at -80°C in the event we decide to measure additional biomarkers related to the study objectives. Archival of blood samples also includes those obtained at screening, both for persons meeting eligibility requirements as well as those who do not meet eligibility requirements. Appropriate notation has been made in the informed consent to alert participants that we will be archiving specimens and that they have the right to refuse our use of these specimens for future analyses. Lastly, approval from the OSU IRB will be sought via a protocol amendment prior to the analysis of any additional biomarkers not specified herein.

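### The Medical Safety Plan puts participants face down (prone) for every blood draw and calls this ideal if they faint; supine was most likely meant.

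*Protocol*

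**What the plan says.** Section III.F of the protocol (Medical Safety Plan) gives the only instruction on body position: "all blood collection procedures throughout each study visit will occur while positioned on a hospital bed in the prone position". It is introduced as a measure for participant safety and is said to follow the group's previous studies.

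The next sentence gives the reason. Participants who feel weak or dizzy, or who faint, are covered because "they would already be ideally positioned to minimize risks associated with these symptoms".

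The section then describes what staff do. For recovery: "Participant status (e.g. attentiveness, skin color) will be monitored in our clinical laboratory to ensure recovery". For a faint: "if a participant were to faint, then smelling salts would be administered along with a carbohydrate-containing food upon regaining consciousness".

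The sampling schedule is in section III.D (Detailed Study Procedures). Blood is taken "Once at screening (8 mL), and 11-times during each pharmacokinetic trial". On day 0 there is a fasting draw before the meal, and then "blood samples will be collected at 3, 4.5, 6, 7.5, 9, and, 12 hours post-meal ingestion". The draws at 24, 48 and 72 h are fasted. The 36 h draw is not: "They will return again for a non-fasting blood draw at 36-h post-meal ingestion".

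**The concern.** In clinical use prone means lying face down. That does not fit the stated reason for the position or the first aid that follows it. Smelling salts are held near the nose, and food is given by mouth. A participant who faints while face down has to be turned, or at least have the head turned, before either can be given.

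This is an operative safety instruction and not background text, and it applies to every draw. Followed literally, it adds a step before first aid for fainting, one of the fasting-related risks that III.F sets out to manage. What is at stake is participant safety and a protocol that agrees with itself. No endpoint, sample-size or analysis question depends on it.

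**Working it through.** **Text check.** The issue is one of wording, so the main check sets the statements of III.F side by side.

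| Statement in III.F | Fits face down? | Fits face up? |
|---|---|---|
| On a hospital bed, so less injury from a fall | Yes | Yes |
| Ideally positioned if the participant faints | No: must be turned before first aid | Yes |
| Smelling salts, then food on waking | Not without turning | Yes |
| Staff watch during visits for signs such as confusion and fainting | Harder, face hidden | Yes |
| Attentiveness and skin color followed during recovery | Not tested: nothing keeps the participant prone by then | Yes |

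Four of the five rows carry information about orientation or access. The first row supports lying down but does not separate the two orientations. The last row is weak evidence, because the monitoring it describes belongs to the recovery phase. The second and third rows decide the matter.

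Both documents were then searched for any other body position for blood draws. There is none. The word supine does not appear, and no reason is given for a deliberate face-down position.

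**Coverage.** Inputs are the sampling times in III.D and the number of trials per study (6 in Study 1 and Study 3, 4 in Study 2).

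- Draws per trial: 0, 3, 4.5, 6, 7.5, 9, 12, 24, 36, 48 and 72 h = 11, which matches the protocol's own count.
- Cross-check against the stated blood volumes: 7 × 16 mL + 4 × 8 mL = 144 mL per trial. With 8 mL at screening, 6 × 144 + 8 = 872 mL and 4 × 144 + 8 = 584 mL. Both agree with III.D.
- Study 1 or Study 3: 11 × 6 = 66 draws per participant.
- Study 2: 11 × 4 = 44 draws per participant.
- Fasted draws (0, 24, 48, 72 h): 4 × 6 = 24 and 4 × 4 = 16.
- Post-meal or non-fasting draws (3, 4.5, 6, 7.5, 9, 12, 36 h): 7 × 6 = 42 and 7 × 4 = 28.
- III.D counts screening as a visit and takes blood there. Including it gives 66 + 1 = 67 and 44 + 1 = 45.

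These numbers show how widely the instruction applies. They say nothing about how often a participant would faint or be harmed.

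**The case against.** The strongest reply is that this is an editorial slip that nobody would carry out. In everyday English prone is sometimes used for lying flat in any direction, and on that reading the paragraph is coherent, if loose. A trained phlebotomist takes the blood, staff are trained in basic first aid, and the set-up is said to match previous studies. Nothing shows that anyone was or would be placed face down.

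Most of that is fair, and it is why the point is minor. It does not clear the text. A safety plan should be correct when read literally, and no other sentence tells the reader which meaning to take.

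Three narrower objections also carry some weight:

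- The recovery-monitoring sentence does not by itself show a conflict, since a participant may be turned by then. The conclusion does not need it.
- The draw counts, and especially the fasted split, have no bearing on which position is right. They describe reach only.
- The SAP is dated 10/01/2025 and describes the analysis in the past tense, so collection may be over. If so, an amendment protects no participant. The protocol would still be wrong as written, and the remedy becomes a clarification.

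**Conclusion.** The concern holds. As written, III.F specifies a face-down position for all blood collection and calls it ideal for a faint, while its own first-aid steps need the face to be accessible.

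The wording itself is certain. That it is a slip for supine is an inference: it rests on the strict clinical meaning of prone and on the lack of any stated reason for a face-down position. The documents cannot confirm what was intended or what was done in the clinic.

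The size is small. The literal consequence is one extra step, turning the participant, before first aid. Lying on a bed still reduces injury from a fall. The controlled diet, close observation, snacks, trained staff and access to emergency services all remain in place. Endpoints, power and analysis are not affected.

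**What to change.** In III.F, replace *prone* with *supine*, or with another face-up reclining position such as semi-recumbent if the clinical staff confirm that this was meant. Section III.D needs no change, because III.F already governs every draw.

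The cost is a one-word protocol amendment, with no added procedure or visit. If sampling is complete, a short note to the record stating the position actually used would serve instead.

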Cover Page

Document: Statistical Analysis Plan

Official Study Title: Achieving Nutritional Adequacy Of Vitamin E With An Egg/Plant-Based Food Pairing

ClinicalTrials.gov ID: NCT04287816

Document Date: 10/01/2025

Statistical Analysis Plan

Power Analysis & Sample Size Determination. Plasma deuterium labeled (d_x) α -tocopherol (α -T) area under the curve from 0 to 72 hours (AUC_{0-72}) was the primary outcome and formed the basis for power analysis. Sample size estimates were derived from a previously published study demonstrating a dose-dependent increase in d_6 - α -T bioavailability with 0–11 g of fat from cream cheese.¹ Using the smallest observed difference in d_6 - α -T AUC_{0-72} —between the 0 g and 2.4 g fat trials—power analysis indicated that a sample size of 5 participants would be sufficient to detect statistically significant differences (90% power, $\alpha = 0.05$; PS Power and Sample Size).

All data (means \pm SE) were analyzed using GraphPad Prism (version 10, GraphPad Software, LLC). Variance was assessed using the Brown–Forsythe test, and data were log-transformed when necessary to meet assumptions of equal variance prior to statistical testing.

Predefined between-treatment comparisons included:

1. Dose-dependent effect of eggs on d_x - α -T pharmacokinetics: SPINACH, SPINACH + 1 EGG_{0 h}, SPINACH + 2 EGGS_{0 h} and SPINACH + 3 EGGS_{0 h}
2. Food matrix effects on d_x - α -T pharmacokinetics: SPINACH + 2 EGGS_{0 h}, SPINACH + WHITE and SPINACH + OIL
3. Meal timing effects on d_x - α -T pharmacokinetics: SPINACH, SPINACH + 1 EGG_{0 h}, SPINACH + EGG_{3 h}, and SPINACH + EGGS_{0 & 3 h}.

Dose-dependent and matrix effect comparisons, which formed the primary objective of the study, were analyzed together using one-way repeated measures analysis of variance (ANOVA), or linear mixed-effects models (LMM) in cases of missing data, followed by Holm–Šidák post hoc tests when a significant main effect was observed ($p < 0.05$).

The meal timing effect, which was the exploratory objective, was analyzed separately using repeated measures ANOVA or LMM in cases of missing data, followed by Fisher’s least significant difference (LSD) test when a main effect was significant ($p < 0.05$).

Reference

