**Achieving Nutritional Adequacy of Vitamins E and K With An Egg/Plant-Based Food Pairing****Executive Summary**

The initial intention of this protocol was to conduct Study 1 and Study 2 as separate investigations, with each study entailing a cross-over design for 4 different 72-h pharmacokinetic (PK) trials. Prior to initiating these plans, the Sponsor provided additional support to conduct an ancillary investigation under *Study 1*, which resulted in a total of 6 different 72-h PK trials; no changes were made to *Study 2* (*i.e.*, 4 PK trials). If participants consented separately to complete both Study 1 and Study 2, this resulted in a total of 10 PK trials. Both during and post-pandemic, our progress to conduct and complete Study 1 and 2 has been impacted. Thus, this revised protocol (submitted Aug 2022) reflects our efforts to gain efficiency in our work and address the study's primary objectives by combining a subset of Study 1 and Study 2 PK trials into a new Study 3 that only involves 6 PK trials. Our intent here is to complete all procedures in participants who are actively involved in *Study 1* and *Study 2*. Those who complete *Study 1* will be invited to reconsent for enrollment in *Study 2*. Thereafter, no new participants will be enrolled in *Study 1* or *Study 2*; all future participants will be enrolled only in *Study 3*. With this plan, we will enroll 5 participants in *Study 1* to ensure fulfillment of primary and ancillary objectives. A maximum of 5 persons will complete *Study 2* and up to 10 participants will complete *Study 3*. Thus, total enrollment across Study 1, 2, and 3 ( $n =$  up to 20) does not increase the number of total participants targeted for enrollment compared with our initial protocol that only involved *Study 1* and *Study 2*. We can therefore achieve study all objectives without increasing overall enrollment, but will be able to reduce participant burden and potential risk.

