We provided the most accurate evidence in humans that  $\alpha$ -T absorption, when administered in an apple matrix, is only 10% when ingested in the absence of fat, and that its absorption increases in a dietary fat-dependent manner up to 33% when co-ingested with 11 g of fat (Fig 2). Pharmacokinetic analysis indicated that the time to maximal plasma concentrations of  $\alpha$ T ( $T_{max}$ ) and its half-life ( $t_{1/2}$ ) were unaffected regardless of the quantity of dietary fat ingested. Higher maximal concentrations ( $C_{max}$ ) of  $\alpha$ -T in response to increasing dietary fat (Fig 2) were therefore attributed to greater intestinal absorption rather than altered gastric emptying. We also observed that fat intakes, within the range of 0-11 g ingested, linearly increased  $\alpha$ -T bioavailability such that 0.43 mg of  $\alpha$ -T was absorbed for each additional gram of fat ingested (Fig 2C). Thus, our planned studies will exploit the highly digestible lipid content of eggs (4.8 g total fat/egg) to demonstrate that eggs dose- and time-dependently improve plant-derived  $\alpha$ T and PQ bioavailability, and more substantially than phospholipid-free vegetable oil. Further, because co-PI [name] is enlisted to hydroponically grow deuterium-labeled spinach, pharmacokinetic responses of both deuterium-labeled  $\alpha$ -T and PQ can be assessed independently of the confounding effects of the low-level amounts of unlabeled  $\alpha$ -T and PQ present in egg yolks or those already present in intestinal or liver tissue.

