#### A. Research Design

Our initial objective was to conduct two separate trials having  $1 \times 4$  study designs (Study 1 (4-arms) & Study 2 (4-arms). Arms 5 and 6 in Study 1 were added to address a secondary objective through an ancillary study. Due to the significant delay in progress caused by the global pandemic, we plan focus the remainder of work on the primary objectives by enrolling only 5 participants, instead of 10, for Study 1 and create a new Study 3 that combines select arms of Study 1 and Study 2 into a succinct  $1 \times 6$  study design. This will avoid the need to re-consent persons to complete Study 2 and overall reduce participant burden.

For the planned studies, we will conduct three separate cross-over studies. The first study consists of a 6-arm cross-over study (Study 1), the second in a separate cohort will be 4-arm crossover study (Study 2), and the third study consists of a 6-arm cross-over study (Study 3). For all studies, healthy adults who fulfill the enrollment criteria will be enrolled from the Columbus, OH area. Studies will be completed in the OSU Human Nutrition Research Center.

For *Study 1*, fasted participants will ingest  $\sim 100$  g of deuterium-labeled steamed spinach with 0, 1, 2, or 3 hardboiled eggs (Study 1 Arms 1-4, respectively). In Study Arm 5, participants will ingest spinach alone followed by 1 egg 3-hours later. In Study Arm 6, participants will ingest spinach with 1 egg followed by another egg 3-hours later. Thus, Study Arms 1-4 will test the dose-dependent effects of eggs on nutrient bioavailability and Study Arms 5-6 (with comparison to Study Arms 1 and 2) will test the ‘timing’-dependent effects of eggs on nutrient bioavailability. For all studies,  $\sim 100$  g of deuterium-labeled steamed spinach (to provide 2 mg  $\alpha$ -T and 500  $\mu$ g PQ) will be administered. Hardboiled eggs will be administered at a dose of 0-3 eggs ( $\sim 50$  g each) to provide 0-14.4 g fat. For each cross-over trial, blood will be collected prior to (0 h) and at 3, 4.5, 6, 7.5, 9, 12, 24, 36, 48, and 72 h post-test meal ingestion to ensure that blood samples are collected at times corresponding to the  $T_{max}$  of  $\alpha$ -T between 10-12 h and  $T_{max}$  of PQ at either 3-5 h or 6-8 h. Plasma and chylomicrons will be collected and archived as we described.

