**Power Calculation.** The quantity of egg-derived fat is similar to that in our report demonstrating a dose-response increase in d6- $\alpha$ -T bioavailability when ingested with 0-11 g of fat derived from cream cheese. Using the smallest difference in d6- $\alpha$ -T Cmax, which occurred between the 0 g and 2.4 g fat levels (**Fig 2A**), our power analysis indicated that only 5 participants would be needed to detect statistically significant differences (90% power, P<0.05; PS Power and Sample Size). Similar powering is also obtained when using d6- $\alpha$ -T AUC0-72 h or absorption (%). Studying so few participants is impractical for establishing dietary recommendations. Thus, for studies 1-3 separate cohorts of 5 adults will be enrolled. By combining participants from all 3 studies, we will have 10 adults under each primary objectives to consider egg-dependent increases in **primary outcomes** (Cmax, AUC, estimated absorption of  $\alpha$ -T or PQ). This increases statistical power to >97% (P<0.01) while allowing for consideration of potential differences between men and women.

**Recruitment.** We will recruit participants through posted flyers, e-mail, electronic and newsprint advertisements (e.g. campus student and faculty/staff newspapers, local and regional newspapers), word of mouth, and social media (e.g. Facebook). The posted advertisements will instruct interested participants to complete an online eligibility survey or call the study center ([name] Laboratory, Department of Human Sciences) to obtain further information. During the phone-in hours, a trained individual (i.e. project coordinator or graduate assistant) will be available to describe the study and determine preliminary qualification by conducting a scripted phone interview (e.g. do you take dietary supplements?, do you smoke?; see *Phone Script* attachment). The individual will record answers and assess whether or not the person calling is likely or not to be an acceptable study participant. If the caller and the interviewer agree that the caller should participate, the prospective participant will be invited to a screening meeting, where the study will be fully described and the individual will be provided a consent form to complete prior to any

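### A variance pre-test that ignores the crossover pairing guides whether the primary AUC0-72 is logged, so the scale of the primary result depends on the data

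*SAP*

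**What the plan says.** The SAP states that labelled α-tocopherol AUC0-72 "was the primary outcome and formed the basis for power analysis". Its data-handling paragraph, which covers all data, names the Brown–Forsythe test as the check on variance and adds that "data were log-transformed when necessary to meet assumptions of equal variance prior to statistical testing". It gives no p-value cut-off, no default scale and no analysis on the other scale.

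The dose and food-matrix comparisons are analysed together by one-way repeated measures ANOVA, or by a linear mixed model (LMM) if data are missing, with Holm–Šidák tests after a significant main effect. The exploratory meal-timing effect "was analyzed separately using repeated measures ANOVA or LMM in cases of missing data". SPINACH and SPINACH + 1 EGG belong to both analyses.

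The SAP states a sample size of 5. The Protocol (B. Sample, Power Calculation) says: "By combining participants from all 3 studies, we will have 10 adults under each primary objectives". The timing arms exist only in Study 1, for which the Protocol plans on "enrolling only 5 participants, instead of 10, for Study 1". The Protocol's Anticipated Data Analysis Plan contains no transformation rule. Neither document mentions sphericity or a correction for it.

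**The concern.** Every arm is measured in the same participants. Brown–Forsythe is a one-way ANOVA on absolute deviations from arm medians and treats those arms as separate groups. Repeated measures ANOVA without a correction needs something else: equal variance of the within-person differences. Passing the check gives no assurance on that.

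The larger issue is the scale. On the raw scale a contrast is a difference in AUC; on the log scale it is a ratio. The two can disagree on whether a contrast is significant, and the plan lets the data guide which is used. If the check is run separately for each analysis, the SPINACH vs SPINACH + 1 EGG contrast could appear on one scale in the primary analysis and on the other in the timing analysis.

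**Working it through.** **1. The plan's own figure.** The documents give no AUC0-72 difference or SD, so n=5 cannot be recomputed forward. Solving backwards (paired t-test, two-sided 0.05, 90% power, n=5) gives a standardised difference of 1.97. At n=10 and α=0.01 that effect has 99.2% power, consistent with the Protocol's >97%. This is coherent, but it says nothing about scale or variance.

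**2. What each method examines.** Brown–Forsythe takes Z = |Y − arm median| and forms F on k−1 and k(n−1) df. For k=6 arms that is 5 and 24 df at n=5, and 5 and 54 df at n=10. Nothing in it links a participant's arms. With truly equal normal variances its rejection rate falls from 0.3% to 0.0% at n=5, and from 3.0% to 0.1% at n=10, as the within-person correlation rises from 0 to 0.8.

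Sphericity concerns Var(Yi − Yj) = σi² + σj² − 2ρσiσj. Set every σ to 1. With ρ=0.9 the variance of a difference is 2(1−0.9)=0.2, and with ρ=0.3 it is 2(1−0.3)=1.4. That is a sevenfold spread with identical arm variances.

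**3. Inputs for the power check (assumed unless a source is given).**
- Means: Protocol, Background: absorption is 10% without fat, and "its absorption increases in a dietary fat-dependent manner up to 33% when co-ingested with 11 g of fat". Slope (33−10)/11 = 2.09 points per g. At 4.8 g fat per egg this is about 10 points per egg, so the means are 10, 20, 30 and 40 for 0–3 eggs. Three eggs (14.4 g) extrapolates beyond 11 g, and absorption from fortified apple stands in for spinach AUC.
- Oil: 25% below 2 eggs, 0.75×30 = 22.5. Egg white: 10 or 15.
- Lognormal person and residual effects; within/between CV 20/30, 30/30 and 30/50%.
- Brown–Forsythe cut-off 0.05.
- Holm–Šidák over 9 pairs (6 dose, 3 matrix) after a Geisser–Greenhouse ANOVA at p<0.05; complete six-arm data.

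At 30/30% the total CV is √(1.09×1.09 − 1) = 0.434. The raw SD runs from 4.3 at mean 10 to 17.3 at mean 40, while the log SD is the same in every arm.

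**4. Power for SPINACH vs SPINACH + 1 EGG.**

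| n | Logs triggered | Error term | SAP rule | Fixed log |
|---|---|---|---|---|
| 10 | 42–70% | pooled | 67–99% | about 100% |
| 10 | 42–70% | pair-specific | 82–100% | 97–100% |
| 5 | 4–9% | pooled | 14–63% | 81–100% |
| 5 | 4–9% | pair-specific | 11–52% | 34–82% |

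At n=5 the check misses a fourfold spread in SD and behaves almost as a fixed raw analysis.

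**5. Type I error of the rule.** With all means equal (between/within CV 30/20 or 50/40%), the overall test under the rule rejects in 3.2–4.7% of runs.

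**6. If variation is additive instead.** With residual SD 2.5–4, person SD 2–3, the same means and n=10, the check keeps the raw scale in 97–99% of runs. Fixed log with pair-specific error loses at most about 3 points of power. With pooled error the loss can be large: 2 vs 3 eggs falls from about 99% to 24% in the worst setting. The 3-point figure holds only for n=10. Running the same additive settings at n=5 (6,000 runs; residual SD 4, person SD 3, egg white 10) takes SPINACH vs SPINACH + 1 EGG from 61% on raw to 31% on log with pair-specific error.

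**7. Sphericity.** Take equal arm variances, correlations 0.8–0.9 within and 0.3–0.6 across the low-fat (spinach, egg white) and fat-containing arms, a true null and n=10. Uncorrected ANOVA rejects in 7–12% of runs and Geisser–Greenhouse in 4–5%; Brown–Forsythe flags 1–2%. A random-intercept LMM with 5 participants on Study 1 time-0 arms, 5 on Study 2 arms and 5 on all six rejects in about 5–10%.

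**The case against.** The best defence is that the check usually picks a sensible scale. It keeps raw when variation is additive and, at n=10, often logs when SD grows with the mean. That stands, and it means fixing the raw scale would not be an equal cure. With SD proportional to the mean, one n=10 setting (between/within CV 40/30%, means 10 to 33) gives SPINACH vs SPINACH + 1 EGG 46% power on raw and 97% on log.

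Second, the main dose contrasts barely move at n=10: SPINACH vs 2 or 3 eggs differs between the rule and fixed log in at most 2% of runs (pooled) or 7% (pair-specific). This also stands, for n=10.

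Third, the SAP says only that logs were used when necessary. The 0.05 cut-off is assumed; at 0.01 logs are triggered in 19–42% of n=10 runs, and at 0.10 in 57–83%. With a small effect (+15% per egg) the figure is 2–6%. The sizes are therefore illustrative.

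Fourth, the Protocol reports a linear rise with fat, which makes a raw scale defensible. But a linear mean says nothing about how the variance behaves, and the ANOVA fits a separate mean to each arm on either scale.

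Fifth, the SAP never offers Brown–Forsythe as a sphericity check. That is right, and the sphericity point is secondary for that reason.

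**Conclusion.** The point holds as a matter of power and interpretation. The SAP leaves the scale of its primary result to a variance check unsuited to paired data, with no cut-off or default. If SD is roughly proportional to the mean, the cost for SPINACH vs SPINACH + 1 EGG at n=10 is up to about 33 points of power with pooled error (100−67) or 15 with pair-specific error (97−82), and it is larger with pooled or pair-specific error at n=5. These sizes rest on assumed means, CVs and cut-off, and on complete six-arm data.

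A reader might infer more than the documents support:
- *The check inflates type I error.* It does not; the rule stays at 3.2–4.7% under the null.
- *The check is harmless at n=5 because it rarely fires.* Rarely firing is the problem there, since the analysis defaults to raw.
- *No sphericity correction was used.* The SAP is silent, which is not the same. The 7–12% applies only to uncorrected complete-data ANOVA.
- *The number of listed contrasts that change measures the harm.* That count mostly reflects the gap between raw and log analyses, not the effect of the check.

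**What to change.** - Drop the Brown–Forsythe check. Analyse AUC0-72 on the log scale in both the primary and meal-timing analyses, and report geometric mean ratios with confidence intervals.
- Use pair-specific error for the post hoc contrasts, and say so.
- Report the raw-scale analysis as a labelled sensitivity analysis.
- Because the SAP is written in the past tense (dated 10/01/2025), disclose which scale was originally used. Naming a scale now cannot restore pre-specification, so results on both scales must be visible.
- State that Geisser–Greenhouse is applied to complete-data repeated measures ANOVA. For the LMM, name a covariance structure that does not assume compound symmetry, or a robust method; a random participant intercept alone does not address non-sphericity. An unstructured six-arm covariance has 6×7/2 = 21 parameters, so a fallback should be named.

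The work is a change of SAP wording and a re-run. The statistical cost depends on n. At n=10, pair-specific error gives up little on the log scale (97–100% against about 100%), and fixed log loses at most about 3 points if variation is additive. If only 5 participants contribute, pair-specific error costs more (34–82% against 81–100%), and so does logging additive data. The raw-scale results then carry more weight and should be shown beside the log-scale results.
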